Recruitment: All study patients will be initially identified by research assistants who will review both (a) all new admissions to the relevant inpatient units in each study centre twice daily; and, (b) all referrals for chest drainage insertion at each centre. It is anticipated that most drains at both sites will be inserted by interventional radiologists, although a minority may be inserted by general surgeons. Physicians and radiologists/surgeons will also be asked to notify the site research assistant and/or site investigator of children admitted with pleural empyema who may be eligible for the study. Patients will be approached, eligibility criteria confirmed, consent obtained, and enrolled after the decision to refer for chest drainage but before chest drain insertion occurs.

Randomization – Sequence generation, allocation concealment and implementation: After informed consent is obtained, patients will be randomized into treatment groups using a random allocation sequence facilitated by the Applied Health Research Centre (AHRC), which will be the coordination and management centre for the trial and administered by the hospital research pharmacies. Randomization will be stratified by centre. Blocking will be used to ensure that the two comparison groups are about the same size throughout the trial for each center and for the trial as a whole (about 49 per group). An allocation ratio of 1:1 with random block size will be used within each stratum (centre). This will help to ensure that clinicians, investigators, or outcome assessors will not decipher the block size. A computer-based pseudo-random number generator will be used to create treatment allocation tables for each study center. After patient eligibility has been confirmed and consent obtained and just as the patient leaves the inpatient unit to the radiology suite or operating room for chest drain insertion, the site investigator, or his/her delegate, will assign the patient a unique study identification (ID)

number in sequential order. The study ID will correspond with the randomization table held in the research pharmacy for dispensing blinded DNase or placebo. The biostatistician will maintain a secure master list of the randomization codes and the assigned treatments will be checked against the master list at the end of the study.

Blinding: Patients, their parents or other caregivers, site investigators, research assistants and coordinators, treating physicians (pediatricians, radiologists, and interventional radiologists or surgeons), treating nurses, and data managers will be blinded to the treatment allocation. Group allocation will be concealed until the final data analysis is performed. Intervention drugs will be blinded by the research pharmacy. Both arms will be constituted by the research pharmacies in clear liquids in a polyethylene container⁴² in a manner such that both are identical (packaging, colour, volume, texture, and odour) to ensure blinding. After obtaining the treatment number from the central randomization centre, the study pharmacist will retrieve the corresponding vial and one of its treatment number labels will be attached to the patient's case report form (CRF).

Unblinding Procedures: We do not anticipate any circumstances that would require unblinding as knowledge of study arm is not anticipated to affect any treatments for patients.

Data collection methods: Data collection for outcome measures will be mainly collected in hospital by the Research Assistant (RA). At baseline, the following data will be obtained: age, sex, duration of antibiotic treatment prior to chest drainage insertion (days), duration of fever prior to chest drain insertion (days), hypoxia in room air (oxygen saturations less than 92% in room air prior to intervention), microbiologic identification of causative agent (blood culture results, throat swab, pleural fluid culture, pleural fluid PCR), ultrasound of chest: pleural effusion size >10 mm <10 mm, stage of empyema on ultrasound of chest: Stage 1: anechoic nonseptated fluid; Stage 2: echoic fluid without septation; and Stage 3: septated fluid and Stage 4: septations with solid appearing components comprising more than one third of the effusion.⁵³ All ultrasounds will be reviewed by a blinded study radiologist (BC). In addition, patients will receive a follow-up phone call from the RA at 3 months enquiring about any possible readmissions and ongoing symptoms of fever, shortness of breath and/or exercise intolerance.

Data management: The Applied Health Research Centre (AHRC) of the Li Ka Shing Knowledge Institute of St. Michael's Hospital will serve as the data management centre under the direction of co-investigator [name]. AHRC employs state-of-the-art web based data management software, Medidata RAVE™ (5.6.3), a secure encrypted web based clinical trial data management system which is fully configurable and incorporates sophisticated data validation rules to ensure high quality data capture. RAVE™ allows for remote web-based data entry directly from the hospital sites, facilitating real time data access.

Statistical Analysis:

Baseline characteristics: Patient characteristics and descriptive variables will be presented for each treatment arm: age, sex, duration of antibiotic treatment prior to chest drain insertion (days), duration of fever prior to chest drain insertion (days), hypoxia, defined as saturations in room air less than 92% (yes/no), bacterial identification and subtype, pleural effusion size on ultrasound (>10 mm, <10mm), stage of empyema on ultrasound (frequency). For continuous variables, means and standard deviations (SD) or medians (inter-quartile ranges) will be presented. For categorical variables, proportions will be presented.

Primary outcome: Data will be analyzed according to intention to treat principles for the primary outcome (e.g. patients who do not receive all three doses of study drug will be analyzed in the group they were assigned to). Exceptions to this principle will only include any patient who dies in hospital and will be excluded from the analysis of time to hospital discharge. Given that the primary outcome and other acute secondary outcomes are obtained during hospitalization, it is anticipated that there will be no missing data for these outcomes with the possible, but unlikely exception of in-hospital death, which is rare in childhood empyema. For the follow up outcomes at 3 months, the proportion of patients who follow up will be presented for each treatment arm, and patients who are lost to follow up will be stated but omitted from the analysis. The primary outcome, time (in days) to hospital discharge, will be described as the difference between the two means with the 95% confidence intervals. The student's t-test (independent two sample test assuming equal group size and variance), will be used to detect a difference between the two treatment groups. If the resulting data is inappropriate for a t-test (increasing variance with the mean is the biggest concern since the test is quite robust to non-normality in the population), a suitable transformation or non-parametric test may be used. If feasible, a secondary analysis of the primary outcome will analyze time to discharge, treating death as a competing risk, using methods for survival data. Since randomization is stratified between five centres, the analysis will adjust for this stratification by including centre as a covariate in a multiple linear regression model, to obtain adjusted treatment effects. Additionally, a treatment by centre interaction will be tested to see if the treatment effect differs between centres. Subgroup analyses will also be conducted to explore any potential differences in outcomes by age or sex.

Secondary outcomes and exploratory outcome: For the secondary and exploratory outcomes that are continuous variables (e.g. duration of drain insertion, hospital stay after intervention to meeting discharge criteria, duration of fever after the intervention, amount of hemithorax occupied by pleural effusion in radiographs) the difference between the two means with the 95% confidence intervals will be presented. The student's t test will be used to detect a difference between the treatment groups. Dichotomous outcomes (serious bleeding, need for further interventions, need for ventilatory support, mortality) will be described as the absolute number and proportion. A Fisher's exact test will be used to detect a significant ($p < 0.05$) difference between the two treatment arms. The treatment effect will also be presented as the relative risk with 95% confidence intervals. These analyses will be viewed as hypothesis generating, and therefore, no correction for multiple testing is planned.

Data Monitoring and Safety: Data monitoring will be conducted with a Data Monitoring Committee (DMC) composed of a pediatric hospitalist, a respiratory physician and an interventional radiologist. The DMC will be completely independent of the investigators, and will be provided with clinical information from the trial case report forms for death, surgical events and adverse events, including those that were described in the adult DNase trial (hemoptysis, gastrointestinal bleeding, chest pain, nausea, transient confusion and rash). The DMC will be able to request additional information from clinicians.

Adverse Event Reporting: All serious unexpected adverse events will be reported to the REB; as per SickKids REB guidelines. All serious adverse drug reactions to the study medication will be reported to Health Canada within 15 calendar days or for death or life-threatening events, within 7 calendar days. In the latter case, a follow-up report will be filed within 8 calendar days. Adverse reactions will be managed according to the standard clinical management practices. All adverse events and adverse reactions will also be reported to the PI within 24 hours.

[figure not shown]
Quality Assurance: This project will be monitored by The Applied Health Research Centre (AHRC) during the data collection phase of the project. The aim is to ensure that all researchers are maintaining

the highest ethical, scientific and safety standards for all study participants, and are in compliance with all relevant policies, provincial and federal legislation, and international guidelines such as ICH- Good Clinical Practice. All studies are categorized according to the Continuing Review Matrix based on the type of study and the level of risk (I to IV) to research subjects and the Clinical Research Monitor will review at minimum 10% of the research subjects' records for study eligibility, informed consent, adherence to study protocol, reporting of adverse drug reactions and adverse events, and data quality including computer database security and storage of records. Findings of the will be presented to the Research Ethics Board and lead PI in a written report, and specific recommendations arising from the report will be implemented in a timely manner.

ETHICAL CONSIDERATIONS: Informed consent will be obtained from parental caregivers. Given the young age of children with empyema (average age of 4 years), it is anticipated that most will not be able to consent/assent to participate. Informed consent/assent will be obtained from all those who are able to provide it. Potential known adverse events from study interventions are mainly local as the drugs are not systemically absorbed and include intrapleural bleeding, rash, voice alteration, chest pain and laryngitis. Aside from receiving the study interventions, participation will require parents to agree to be contacted by research personnel for a short (< 5 min) phone call three months post-discharge.

Feasibility and Timelines: Internal data from decision support services at the three participating hospitals indicates that in fiscal year 2010-11, there were a total of 92 children with chest drains inserted for pleural empyema (25 at Sainte Justine, 33 at CHEO and 34 at SickKids), and, in 2009-10, 98 children received a chest tube (28 at Sainte Justine, 37 at CHEO and 33 at SickKids). Based on a review of the patients who had chest drains inserted at SickKids from 2008-2011, less than 5% of these will be ineligible for this trial (e.g. due to a comorbid condition such as cerebral palsy). Thus, it is anticipated that a total of 180 potentially eligible patients will be available for recruitment, at three of the five sites, over two years for this clinical trial.

Our previous experience with this population indicates a willingness to participate in research. In an observational study of long-term outcomes in pediatric empyema requiring participants to complete detailed follow-up questionnaires and attend an appointment for physical examination, spirometry and radiography for six months, 88/94 (94%) consented to participate, of whom 6 (7%) were lost to follow-up at one month and a further 8 (9%) at 6 months.

KNOWLEDGE TRANSLATION (KT) ACTIVITIES

KT activities will be facilitated by the leadership of team investigators locally, nationally and internationally. Locally, findings will be presented to clinical groups and incorporated into the empyema Clinical Practice Guidelines at all sites. Nationally, findings will be presented at the Canadian Pediatric Society's Annual Meeting focused on the Hospital Pediatrics Section whose current President is [name] and whose President-elect is [name]. Internationally, we will present findings at the Pediatric Academic Society's Annual Meeting, the largest international pediatric research meeting, facilitated by the Pediatric Research in Inpatient Settings (PRIS) group, an international hospitalist research and KT organization that is co-led by [name]. Given the broad interest in the topic, we anticipate publication of findings in a high-impact general medical or pediatric journal.

IMPACT OF STUDY

Pleural empyema in children has been dramatically increasing in prevalence over the past 10 years and has important short-term morbidity. Unlike in adults, long-term outcome is very favorable and treatment interventions are aimed at reducing the duration of illness. Chest drainage with fibrinolytics has been shown to be an effective therapy in children but duration of illness is still long. This study will examine the effectiveness of adding DNase to see if it results in clinically meaningful improvement in outcomes. The study brings together a group of clinician-investigators with a track record of scholarly work focused on expanding the evidence base for managing this common condition together with researchers with expertise in clinical trials methodology. The results will answer an important clinical question and guide implementation of the most effective therapy for children with pleural empyema.

References

[figure not shown]
Version June 29, 2017.

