Despite the utilization of fibrinolytics, pleural drainage can still be challenging leading to prolonged hospital stays with a painful chest tube *in situ* and ‘treatment failure’ whereby pleural disease persists that cannot be drained necessitating salvage procedures such as open thoracotomy. The need for subsequent procedures is somewhat centre dependent, and, in clinical trials of tPA in childhood empyema, ranges from 17%³¹ to 38%,³² but such procedures are associated with significant morbidity including pain and a variety of potential surgical complications. One potential explanation for both the inadequate drainage leading to prolonged hospital stays and the phenomenon of ‘treatment failure’ is the presence of extracellular uncoiled DNA liberated from dead leukocytes and other bacterial components. Such residual material may increase viscosity, permit biofilm formation, and thus interfere with drainage.³³⁻³⁶ Fibrinolytic agents are not thought to reduce pleural viscosity, but recombinant human DNase has been shown *in vitro* to help decrease the viscosity by cleaving free DNA and hence liquefying parapneumonic pus.^{37,38} Subsequent animal studies have demonstrated that

the combined effects of tPA and DNase in a rabbit model of empyema is more effective than either agent alone.³⁹ Small human (adult) case series have also described benefit from the addition of DNase to the treatment of empyema.^{40,41}

Safety data on DNase is primarily derived from its currently licensed indication, nebulization at a dose of 2.5 to 5 mg once or twice daily for the reduction of sputum viscosity in patients with cystic fibrosis. It is well tolerated with rash, voice alteration, chest pain and laryngitis as common side effects.⁴²

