Clinical Samples at the Hospital for Sick Children: At the SickKids site only, consent will be obtained to store samples of chest tube drainage from subjects. These samples will be used for future testing to determine the microbiological cause of empyema.

Concomitant Medication: Patients in either arm will not receive any intrapleural drug other than directed from this study.

Criteria for discontinuing study interventions: Patients who develop anaphylaxis or serious bleeding (requiring a blood transfusion or resulting in a hemoglobin drop of ≥ 20 g/L) while receiving study interventions will not receive further study drugs. Patients whose chest drains is displaced will only be replaced if clinically indicated for pleural fluid drainage and not for study drug administration alone. Outcomes for all patients who do not received the full study interventions will be analyzed in the group they were assigned to.

Standard care: In keeping with a pragmatic-type trial design, all children will receive standard care for this condition including supportive care, laboratory investigations, imaging, antibiotics, chest drain care and removal and discharge as outlined in the standard care guidelines. Although some variability is expected in care among treating physicians, rigorous randomization and blinding should ensure that confounders are equally distributed between groups. A detailed care map will be adapted from the existing clinical practice guideline co-authored by team investigators (EC and SM) together with the Canadian Pediatric Society. Specific elements in the care plan include:

- a) *Antimicrobial management* - Patients in both treatment arms will receive standard therapy for pleural empyema in children as directed by the responsible physician and standardized guidelines. All participating hospitals currently recommend a 2nd or 3rd generation cephalosporin (cefuroxime or ceftriaxone or cefotaxime) as the empiric antimicrobial therapy with possible addition of clindamycin or vancomycin if *S. Aureus* is a suspected etiology. It is expected that antibiotic regimens will be tailored in line with local microbiology advice.
- b) *Drain insertion* - Chest drains will be placed using an image guided percutaneous technique by interventional radiologists or by a surgeon using a standardized technique under anesthesia agreed upon by all sites. The recommended size of catheter drain used will be an 8 or 10 French pigtail catheter.

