- a. *Time to meeting discharge criteria:* This is defined as the time, measured in hours, and reported in days rounded to a single decimal point, from insertion of the chest drain to meeting discharge criteria. This will be assessed by a research assistant on a twice daily basis (9 AM and 4 PM) and defined as: no fever (temperature less than 38°C) for 24 hours, normal respiratory rate for age [using the World Health Organization (WHO) age-specific criteria (< 50 breaths/min for 2-12 months, < 40 breaths/min

for 1 to 5 years, and < 20 breaths/min for ≥ 5 years)], no hypoxia (transcutaneous oxygen saturations in room air less than 92%), and drinking fluids well.

b. *Time to drain removal*: This is defined as the time, measured in hours, and reported in days rounded to a single decimal point, from drain insertion to drain removal.

c. *Duration of fever after intervention*: This is defined as the duration, measured in hours, and reported in days rounded to a single decimal point, of fever (defined as temperature $>38^{\circ}\text{C}$ taken by any method) from insertion of the chest drain until resolution. This will be recorded by a research assistant daily.

d. *Need for ventilatory support or non-invasive ventilation following the intervention*.

e. *Serious bleeding*: This is defined as intrapleural bleeding resulting in a drop in hemoglobin of greater than 20 g/L or needing a transfusion.

f. *Need for further interventions*: This is defined as the need for further intervention such as placement of another chest drain (by any technique) or surgical intervention such as thoracotomy and decortication, video-assisted thoroscopic surgery, or pneumonectomy.

g. *Hospital readmission*: Any hospital readmission after discharge from hospital for initial treatment for pleural empyema within three months related to pleural empyema or its treatment (e.g. harm). All hospital readmissions will be categorized as empyema-related or not.

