Exploratory outcome – chest radiography: In the aforementioned DNase trial in adults, changes in pleural opacity, measured as the percent of the hemithorax occupied by effusion on day 7 compared with day 1 was a primary outcome. In pediatric empyema, this outcome is problematic because: (a) many children will be discharged prior to day 7; (b) hemithorax size differs substantially across different sized children; and, (c) requiring an additional chest radiograph may be a substantial disincentive for parental caregiver to provide consent participate particularly given the rising concerns of ionizing radiation in developing children. Further, radiographic changes are considered surrogate measures of clinical changes as they often lag behind clinical improvement. There is currently no standard as to the timing of radiographs in hospital, but it is our experience that virtually all children will have a radiograph performed shortly before and/or shortly after chest tube removal. The

Version June 29, 2017.

radiograph closest to the time of drain removal will be reviewed by a blinded study radiologist (BC) to determine the percentage of hemithorax occupied using a 5 point ordinal scale utilized in previous studies ranging from no fluid present to fluid occupying >75% of the most affected hemithorax. Given that radiographic improvement is time dependent, we do not have any *a priori* hypotheses about the results of this outcome across groups (i.e. those with the worst outcomes (chest drain duration) may potentially have better radiographs at the time of drain removal).

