Sample size: The primary endpoint is time to hospital discharge after intervention. The mean time to hospital discharge after chest tube insertion and fibrinolytics varies. Published studies with treatment arms that have included chest drain with fibrinolytics as the primary mode of insertion reported hospital days after the intervention from 6 to 15 days.^{23,24} Hospital length of stay tends to be shorter in published RCTs compared with observational studies of empyema, and the most recently published RCT using an identical tPA dosing regimen to that which we are proposing described a mean (SD) stay of 6.8 (2.9) days.³¹ The desired power for the current proposal is 90% to detect a difference of 2 days in the mean time to hospital discharge between the treatment arms. Based on discussions with clinical experts in the field, hospital administrators and parents of children with pleural empyema, it is believed that a 2 day difference between treatment groups is a minimal clinically meaningful difference, and this has been used in previous empyema trials.²⁷ The adult DNase trial found about a 50% difference in length of stay between treatment and placebo groups.⁴²

Sample size was thus calculated assuming a type 1 error rate of 0.05 (2 sided), power (1-β) of 90%, a standard deviation of 2.9 days for each group to detect a difference of 2 days to be 46 per group. Calculations were performed based on a t test of independent groups. While we do not anticipate any post-randomization ineligibility, for example from misdiagnosis, we will increase the sample size by 5% to account for this possibility (total of 49 patients per group). There will be no other adjustment to the sample size requirements due to loss to follow-up for the primary outcome as the primary outcome is assessed in hospital where the research coordinator will be able to ensure complete data collection.

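### Do the unspecified drain in time to drain removal and the two wordings of fever duration call for a change to the plan?

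*Combined protocol and SAP*

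**What the plan says.** **Drain time.** Under Outcomes – Secondary outcomes, item b, the measure is hours, given in days "rounded to a single decimal point, from drain insertion to drain removal". The list of secondary research questions names the outcome without defining it. Two other places foresee that the first drain may not be the only one. The criteria for discontinuing study interventions state: "Patients whose chest drains is displaced will only be replaced if clinically indicated for pleural fluid drainage". Item f of the secondary outcomes counts "placement of another chest drain (by any technique) or surgical intervention" as a need for further intervention. The exploratory imaging outcome depends on the same event: the "radiograph closest to the time of drain removal will be reviewed by a blinded study radiologist".

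**Fever.** Item c of the secondary research questions defines fever duration as a number of days above 38°C, with no starting point. Item c of the secondary outcomes defines it as hours, reported in days to one decimal, from drain insertion to resolution, recorded daily by a research assistant. Resolution is not defined there.

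**Analysis.** The analysis section for secondary and exploratory outcomes lists "duration of drain insertion, hospital stay after intervention to meeting discharge criteria, duration of fever after the intervention" among the continuous outcomes, compared by difference in means and Student's t test. It adds: "These analyses will be viewed as hypothesis generating".

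**The concern.** An outcome definition should give one value per child, and on a literal reading these two may not.

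If only the first drain counts, a drain that falls out or is removed because it failed yields a short, favourable time. If the last removal counts, the same child has a long time. The choice would matter most if the arms differed in how often drains fail, and DNase is proposed partly as a remedy for treatment failure. The background section says: "The need for subsequent procedures is somewhat centre dependent, and, in clinical trials of tPA in childhood empyema, ranges from 17" per cent, up to 38%. Centres might therefore also differ in how many children are affected. The radiograph nearest drain removal could be a film from before or after a salvage procedure.

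For fever, the count of febrile days and the elapsed time diverge whenever fever is intermittent, and the elapsed time depends on what ends it.

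The secondary hypotheses predict that DNase-tPA will reduce both outcomes. At stake is whether those two comparisons mean the same thing at all five centres, and whether a scoring rule could be picked after the results are known.

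**Working it through.** **The plan's own figure.** The only design calculation is for the primary outcome, and it gives the group size used below. A two-sample t test with a 2-day difference, SD 2.9 days, two-sided 0.05 and 90% power solves to 45.17, so 46 per group (power 90.5%). Then 46 × 1.05 = 48.3, rounded up to 49. Both stated figures reproduce, and neither depends on this point.

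**How far the drain score can move for one child** (invented times). First drain out at 72 h, second in at 96 h and out at 168 h:
- first drain: 72/24 = 3.0 days
- total time in place: (72 + 72)/24 = 6.0 days
- first insertion to last removal: 168/24 = 7.0 days

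There are three defensible scores, and the last also counts a drain-free gap.

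**How many children.** The 17% comes from the trial that the Sample size section describes as "the most recently published RCT using an identical tPA dosing regimen to that which we are proposing". 49 × 0.17 = 8.3 per arm. At 38%, 49 × 0.38 = 18.6. Both are upper bounds, because the rates cover all subsequent procedures and a second drain added while the first stays in need not alter the score. The 17% is itself imprecise. That trial had 36 children; assuming 18 had tPA, 17% is about 3 children, exact 95% interval about 4% to 41%.

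**Effect on the comparison.** Let p be the proportion affected in an arm and D the mean gap in days between first and last removal in those children, taken as equal in both arms.
- Shift in an arm mean = p × D
- Shift in the arm difference = (p₁ − p₀) × D, which is 0 when the rates are equal

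D is not in the documents. If it is assumed to lie between 1 and 5 days, an arm mean moves by 0.17 × 1 = 0.17 to 0.38 × 5 = 1.9 days. If one arm is also assumed to have half the other's rate, the difference moves by 0.085 × 1 ≈ 0.09 to 0.19 × 5 = 0.95 days. These are conditional illustrations, not estimates.

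With equal true rates of 17%, the standard error of the rate difference is √(2 × 0.17 × 0.83/49) = 0.076, and 1.96 × 0.076 = 0.149. Those 15 points are ordinary sampling noise between randomized arms. They are not bias created by the definition.

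**Which drain the text points to.** Prior drainage is exclusion criterion 5, so each child starts with one study drain. The primary outcome and secondary outcomes a and c all start at insertion of the chest drain. A later drain is described as another one and is counted as an outcome of its own. Read together, item b most naturally means the study drain. The analysis section's phrase about duration of insertion would also fit total time, so the lean is clear but not conclusive.

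**Fever for one child** (invented times). Insertion at 3 PM on day 0; above 38°C at 8 PM on day 0 and again at 8 AM on day 3.
- count of febrile days: 2
- elapsed time to last febrile reading: 65 h/24 = 2.7 days
- elapsed time to the start of the first 24 h without fever: 5 h/24 = 0.2 days

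**Which fever definition is analysed.** The protocol summary and the analysis section both speak of fever duration after the intervention. That is the title of item c of the secondary outcomes and matches its start at drain insertion. The febrile-day count is a one-line entry in a list of questions. The elapsed-hours version is therefore the one analysed, and only its end point is open. Item a, two entries above, already uses 24 hours below 38°C for the discharge criteria. It is not formally linked to item c but is an obvious anchor.

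**The case for a change.** The best case for a change is that the gap may not be neutral. The adult trial reported surgical referral of 4% with tPA-DNase against 16% with placebo, so equal failure rates should not be assumed. The outcomes carry directional hypotheses and are tested without multiplicity correction. Blinding does not make five centres score alike, and the wording would be cheap to supply.

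Part of this stands: no rule is written for replaced or post-surgical drains, resolution is undefined, and daily recording sits awkwardly with a unit of hours.

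The rest weighs less.
- The 4% against 16% contrast is with placebo. Against placebo, the odds ratios were 0.17 for the combination and 0.29 (not significant) for tPA alone, and tPA alone is the comparator here.
- If DNase does prevent failures, first-drain scoring flatters the control arm and works against the hypothesis. If DNase causes failures, need for further interventions is reported by arm and would show it.
- Randomization is stratified and blocked by centre, so a local scoring habit falls on both arms about equally.
- Last-removal scoring is not plainly better: it counts drain-free gaps, overlaps with need for further interventions and makes the outcome more variable. Ending fever at the last high reading lets one isolated late spike set the value.
- The case report form is not among the documents, so it cannot be said that later removal times go uncollected.

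**Conclusion.** The gaps in wording are real, but they do not call for a change to the plan. For drain time, first drain, last removal and total time in place are each defensible, and choosing among them is a trade-off. For fever, the documents indicate the elapsed-hours definition, and the one-line count is a loose summary of it. Research assistants and data managers are blinded, data are managed centrally, and allocation is concealed until the final analysis. Analysts can therefore settle the drain and resolution rules as routine data handling before any arm comparison is seen, and apply the same rule to the exploratory film.

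The reach on drain time is at most about 8 of 49 children per arm at the cited 17% (about 19 at 38%). The arm difference does not shift if failure rates are equal, and no shift in days can be derived without assuming D. This conclusion rests on both outcomes staying hypothesis generating and on the scoring rules being set before unblinding. The primary outcome, its analysis and the 49 per group are unaffected.
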